Using data retrieved from electronic health records (see below: Data sources) from three European Union member states, i.e. the Netherlands, Denmark, and United Kingdom, we will address the study objectives in

1. A drug utilization study into prescribing patterns including new use of CHCs and calendar-period specific changes in switching of CHCs
2. A cohort study for incidences of VTE

Population, Variables and Data sources:

For the Dutch drug utilization study and cohort study, we will make use of de-identified data obtained through The Dutch Foundation for Pharmaceutical Statistics (SFK), which gathers its data from >95% of community pharmacies in the Netherlands (<https://www.sfk.nl/english>). All women between the ages of 18-49 years with at least one prescription of combined oral contraceptive use in the period from January 2012 through December 2015 will be included, i.e., both new users as well as prevalent users. New users are defined as women who do not have a prescription of CHC in the two years before starting. We will also obtain information on prevalent users of CHC and thereby we can assess all individual changes (switches) in CHC. Prevalent users of CHC are defined as women who used at least one cycle of CHC. Age at initiation and 4 digit postcodes is also available in the SFK database which allows further characterization of CHC users by age and socioeconomic status. The latter information will be retrieved by using information from the Central Bureau of Statistics (CBS), the Netherlands, which keeps record of socioeconomic status by use of 4-digit postcodes. Although SFK does not indicate if women had venous thrombotic disease for which they need to receive anticoagulant treatment, it can be approximated by the first dose of oral anticoagulant (direct oral anticoagulant (DOAC)) or duration of anticoagulant (vitamin K antagonist), which is specific for VTE.

For the Danish drug utilization and cohort study, data will be linked from the following databases: The Danish Civil Registration System (contains data on age, sex, vital status and migration), the Danish National Prescription Registry (outpatient dispensations of CHC and other

medications), and data on income and education at Statistics Denmark. Women between the ages 18-49 years in the period January 2012- December 2015 will be included, i.e. both new and prevalent users.

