A previous UK primary care database study estimated the crude incidence rate of VTE cases per 10 000 women years was 5.9 (95% confidence interval 5.7-6.0) in CPRD and 6.1 (6.0- 6.3) in QResearch (5). In UK around 28% use oral contraceptives and CHC form a substantial proportion of these.

Data analysis:

In order to assess the effects of the review on initiation (new use) as well as on switching of treatment (between January 2012- January 2014 and between February 2014- December 2015), we will perform segmented regression analyses.

For the Dutch part of study, we will calculate the incidence of VTE among the new users of CHC within each calendar window (January 2012- January 2014 and February 2014- December 2015). From segmented regression analysis, we will obtain information on a potential change in the proportion of different types of oral contraceptives in new users separately and grouped according to generation of CHC after the European commission decision (January 2014). Since we have information about the prescription patterns among new users, we can assess whether the changes observed in the proportions of use of each generation is associated with changes in the incidence rate of VTE in women initiating oral contraceptive use. Furthermore, we will study the changes in the incidence of VTE within users of different types (and generations) of CHCs. A change in this incidence over time, may indicate that certain preparations are prescribed to low/high risk individuals. We will stratify analyses on age and socioeconomic status (risk factors of VTE) of the women.

For the Danish and UK part of the study, estimates on the incidence of VTE will be calculated. Overall estimates as well as estimates stratified by risk factors such as age, socio-economic status, BMI (UK only), smoking status (UK only) will be provided. For the Danish and UK data we will compare the age-standardised incidence rates of VTE against the age standardised initiations of oral contraceptives in order to evaluate whether overall changes in CHC use is associated with overall changes in incidence of VTE.

Milestones:

Task	Month
Data extraction and analysis	10
Writing study results for the EMA	3
Writing manuscript for submission to peer-reviewed journal	3

5. Amendments and updates

None

6. Milestones

Milestone	Planned date
Start of data collection (extraction)	31-03-2017
End of data collection (extraction)	31-12-2017
Final report of study results	01-05-2018

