To investigate switching patterns among prevalent users, individuals will be defined as prevalent users if they had at least one prescription of oral contraceptives between 1 July 2011 and 1 August 2015. Prevalent users will be followed until switch of treatment, six months after last prescription, becoming 50 years of age, December 31st 2015, leave the practice or death, whichever comes first.

Oral contraceptives

We will consider each CHC individually and, additional to the analysis of individual types of combined oral contraceptives, in our analysis, we will group CHC together according to generation (i.e., the second generation containing levonorgestrel/norgestimate and ethinylestradiol, the third generation containing gestodene/desogestrel and ethinylestradiol and the newer generations containing drospirenone and ethinylestradiol).

Analysis

For each calendar year, we provide estimates of the number of initiators of each oral contraceptive type and the number of switchers (from one type to another or to a different dose) overall and stratified by age at initiation of CHC (18-24, 25-29, 30-34, 35-39, 40-44 and 45-49 years), social deprivation (Quintiles of Townsend Deprivation scores), body mass index (BMI) and smoking status.

We will tabulate the estimates of new users by 1000 person years at risk including 95% confidence intervals for each calendar year. Similarly, we will provide estimates of switchers by 1000 person years at risk including 95% confidence intervals for each calendar year of the study period.

In order to assess the effects of the review on initiation as well as on switching of treatment (between January 2012- January 2014 and between February 2014- December 2015), we will perform segmented regression analysis.

For our analyses we will be using Stata version 14 or higher.

WP4

Objectives

To assess changes in the incidence rate of VTE among women using CHCs of reproductive age in the Netherlands between January 2012- January 2014 and February 2014- December 2015 and to investigate any measurable association between these changes and the observed changes in CHC use.

Methods

Study population

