Medication use in the SFK database will be used to approximate the occurrence of VTE by using the first dose of oral anticoagulant, which, in case of DOAC use is specific for VTE or the duration of treatment with Vitamin K antagonists. Incidence of VTE is calculated by following the new users of CHC within each calendar window until they experience a VTE, or up to one year.

We will calculate the incidence among the new users of oral contraceptives in general and per type of oral contraceptive (different types and grouped by generation (second, third and newer generations)).

Analysis

We will tabulate the estimates of the annual incidence of VTE including 95% confidence intervals for each calendar window of the study period.

From segmented regression analysis (WP1), we will obtain information on a potential change in the proportion of initiators of each generation of CHC between January 2012-January 2014 and February 2014- December 2015. Since we have information about the prescription patterns among new users, we can assess whether the changes observed in the proportions of each generation is associated with changes in the incidence rate of VTE in women initiating oral contraceptive use.

Furthermore, we can study the changes in the incidence of VTE within users of different types (and generations) of oral contraceptives. A change in this incidence over time, may indicate that certain preparations are prescribed to low/high risk individuals.

Because we have information about the age and socioeconomic status (risk factors of VTE) of these women, we can stratify analyses on these factors.

For our analysis we will use SPSS for Windows, release 23.0.

WP5

Objectives

To assess changes in the incidence rates of VTE among women of reproductive age overall and by CHC-initiation/switching in Denmark between January 2012-January 2014 and February 2014-December 2015.

Study population

For each calendar year of the study period (1 January 2012 to 31 December 2015) we will identify women who were between 18 and 49 years old. Individuals with no previous record of VTE prior to study entry (from 2002 onwards) will be followed until they are recorded with a VTE, become 50 years of age, 31st of December 2015 or they migrate.

Analysis

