We will estimate the incidence rates of VTE by 10 000 person years at risk in CHC-initiators/switchers before and after the EMA recommendation, including 95% confidence intervals for each calendar year of the study period. We provide overall estimates as well as estimates stratified by age at CHC initiation in oral contraceptive initiators.

For each observation window period (January 2012- January 2014 and between February 2014-December 2015) we will compare the age-standardised incidence rates of VTE against the age standardized VTE incidence rates among initiators/switchers of oral contraceptives in order to evaluate whether overall changes in CHC use is associated with overall changes in incidence of VTE.

Analyses will be performed using SAS version 9.2 or higher.

WP6

Objectives

To assess the incidence rate of VTE among women of reproductive age overall and by initiated CHC in United Kingdom between January 2012- December 2015.

Study population

For the estimate of incidence of VTE in CHC users in UK we will make use of anonymized primary care data. For each calendar year of the study period (1 January 2012 to 31 December 2015) we will identify women who were between 18 and 49 years and have been registered for at least two years prior with one of the general practices that contributed data to THIN. Individuals initiated on CHC with no previous record of VTE prior to study entry (from 2002 onwards) will be followed up until they have their first record of VTE, they become 50 years of age, 31 December 2015 or they de-register with the general practice, whichever comes first.

Analysis

We will tabulate the estimates of incident VTE by 10 000 person years at risk including 95% confidence intervals for each calendar year of the study period among women using CHCs of reproductive age in UK. We provide overall estimates as well as estimates stratified by age, social deprivation (Quintiles of Townsend Deprivation scores), BMI and smoking status.

For each observation window period (January 2012- January 2014 and between February 2014- December 2015) we will calculate the incidence among the new users of oral contraceptives in general and per type of oral contraceptive (different types and grouped by generation (second, third and newer generations)).

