From segmented regression analysis (WP3), we will obtain information on a potential change in the proportion of initiators of each generation of CHC between January 2012-January 2014 and February 2014- December 2015. Since we have information about the prescription patterns among new users, we can assess whether the changes observed in the proportions of each generation is associated with changes in the incidence rate of VTE in women initiating oral contraceptive use.

Furthermore, we can study the changes in the incidence of VTE within users of different types

(and generations) of oral contraceptives. A change in this incidence over time, may indicate that certain preparations are prescribed to low/high risk individuals.

Analysis will be performed using Stata version 14 or higher.

WP7

Outline for the study report

The study report will combine the findings from all 6 work packages. Data from three countries will be used to report on the trends in first ever user prescribing in the two years preceding the relevant Commission Decision January 2012 – January 2014 and the period following the decision February 2014 – December 2015 . Furthermore, using different research strategies, we will report on the changes in the incidences of VTE in the different observation windows, separately for each country. The report will provide evidence regarding the necessity of the recommendation to use safer oral contraceptive preparations as it will show whether the implementation of the recommendation was successful and whether it actually affected the incidence of VTE in the target population.

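### WP6 (UK) contradicts itself on whose VTE is counted, and WP4 (Netherlands) counts it only in new users, so WP7's target-population conclusion is unsupported in both countries

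*Protocol*

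**What the plan says.** **UK.** The WP6 objective in section 9.2 reads "To assess the incidence rate of VTE among women of reproductive age overall and by initiated CHC in United Kingdom". The data analysis part of the Abstract (section 4) sets age-standardised VTE rates against age-standardised initiations for Denmark and the UK, "in order to evaluate whether overall changes in CHC use is associated with overall changes in incidence of VTE". The WP6 study population first identifies all women aged 18 to 49 with two years' registration in THIN, then narrows: "Individuals initiated on CHC with no previous record of VTE prior to study entry (from 2002 onwards) will be followed up". The WP6 rates are tabulated among CHC users and new users, and the age-standardised comparison does not appear.

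**Netherlands.** The WP4 objective is "To assess changes in the incidence rate of VTE among women using CHCs of reproductive age in the Netherlands". The method is narrower: "Incidence of VTE is calculated by following the new users of CHC within each calendar window", to VTE or for at most one year. The Dutch source population in the Abstract is "All women between the ages of 18-49 years with at least one prescription of combined oral contraceptive use", so it includes prevalent users but no never-users.

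**Denmark, for contrast.** WP5 follows all women aged 18 to 49 without a previous VTE.

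**Across countries.** Objective 4 (section 8) relates VTE to the results of Objectives 1 to 3, and Objective 2 is switching among prevalent users. WP7 says the report will show whether the recommendation was implemented and "whether it actually affected the incidence of VTE in the target population".

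**The concern.** Section 7 describes a decision that gave patients information on risk factors, told professionals which types carry the lowest risk, and stated that CHC is contraindicated with one serious or several risk factors. Such a decision can act through product choice at initiation, through not starting, and through switching or stopping in women already on CHC. A VTE rate among initiators responds to product choice at initiation. It does not register women who leave the denominator by not starting, or established users who never enter it.

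For the UK this is a contradiction in the Protocol: the objective and the Abstract need a rate that the stated cohort cannot supply. An analysis plan could not settle it without overriding the cohort definition. For the Netherlands the cohort is narrower than its own objective. At stake is the conclusion in WP7, which is worded for the target population while the VTE data in two of three countries cover initiators.

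**Working it through.** **The plan's own figures.** The only expected VTE count stated is Danish: 300 000 × 4 years × 4/10 000 = 480, which reproduces. Dutch switches: 0.16 × 1 300 000 = 208 000, against about 212 000 stated, which is consistent with rounding of the 1.3 million. No expected VTE count is given for WP4 or WP6.

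**Inputs.** The risk table in the Abstract gives annual VTE per 10 000 women:
- non-users, not pregnant: 2
- levonorgestrel, norethisterone or norgestimate: 5–7 (midpoint 6)
- drospirenone, gestodene or desogestrel: 9–12 (midpoint 10.5)

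The product mixes and the size of each change below are assumptions. The Protocol gives none.

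**1. Fewer starters, same mix.** Take 100 000 would-be starters, half in each product group.
- Before: 50 000 × 6/10 000 + 50 000 × 10.5/10 000 = 30 + 52.5 = 82.5 VTE, a rate of 8.25 per 10 000.
- 10% do not start, drawn evenly: 0.9 × 82.5 + 10 000 × 2/10 000 = 74.25 + 2 = 76.25.
- Change in VTE: (76.25 − 82.5)/82.5 = −7.6%.
- Initiator rate: 74.25/90 000 = 8.25 per 10 000, unchanged.

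In general the fall is 0.1 × (1 − 2/m), where m is the mean initiator rate. With m from 5 (all lower-risk, bottom of range) to 12 (all higher-risk, top of range) it runs from 6.0% to 8.3%, so the assumed mix matters little.

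**2. Fewer starters, all from the higher-risk group.** VTE: 30 + 42 + 2 = 74 (−10.3%). Initiator rate: 72/90 000 = 8.0 per 10 000 (−3.0%).

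**3. All women aged 18–49.** Rate = (1 − u) × 2 + u × [h × 10.5 + (1 − h) × 6], where u is the share using CHC and h the share of users on higher-risk types. Take u = 28% (the Protocol's UK figure for all oral contraceptives) and assume h = 40%.
- User rate: 0.4 × 10.5 + 0.6 × 6 = 7.80.
- All women at u = 28%: 0.72 × 2 + 0.28 × 7.80 = 3.62.
- All women at u = 22%: 0.78 × 2 + 0.22 × 7.80 = 3.28.
- Ratio in all women 0.90 (0.89–0.92 over the table's ranges); ratio in users 1.00.

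**4. What a user-only rate does detect.** If h falls from 40% to 25% with use unchanged, the user rate goes from 7.80 to 0.25 × 10.5 + 0.75 × 6 = 7.125, ratio 0.91 (0.87–0.96 over the table's ranges).

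**5. Secular trend.** A 10% fall in VTE for unrelated reasons gives a user rate of 0.9 × 7.80 = 7.02. A mix shift gives the same crude rate at h = (7.02 − 6)/4.5 = 23%.

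**The case against.** A reader might infer that Objective 4 cannot be answered at all in these two countries. The documents do not support that. Objective 4 asks for between-period differences and any association with changes in use, and names no whole-population denominator. WP4 and WP6 plan rates per window in initiators, by type and generation, set against the change in generation shares. Step 4 shows that this design detects a mix shift.

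Nor is it right that VTE after switching or stopping is always lost. Neither work package states censoring at a switch or stop, so initiators who change stay in follow-up: up to one year in WP4, and to the end of 2015 at the latest in WP6. Their VTE is counted, though not attributed to the change. The gap is women already established on CHC before entry, and women who do not start.

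A fall in starting would also show in the initiation numbers and rates of WP1 and WP3. In step 1, number times rate recovers the fall from 82.5 to 74.25 among starters. But that is a derived figure which no work package plans. It leaves out VTE in the women who did not start and says nothing about established users.

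On secular trend, the planned within-type rates over time are a partial check: a pure mix shift leaves them stable, whereas a general trend moves them all. The Protocol, however, reads such movement as a possible sign of selective prescribing, so the check does not isolate a trend.

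It is tempting to turn the roughly 212 000 Dutch switches into a count of VTE averted. That figure covers switches of every kind in any two years, and the Protocol gives no share moving from higher- to lower-risk types. No count is claimed here.

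Finally, initiator cohorts have a sound rationale. The study-size text puts the risk increase at 13-fold in the first three months and 8-fold over the first year. This argues for reporting new users separately, but not for drawing a population conclusion from them alone.

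**Conclusion.** The point holds for the scope of the VTE cohorts. As written, WP6 cannot produce the overall UK rate that its objective and the Abstract require, and it drops the promised comparison. WP4 is narrower than its objective. Both can answer Objective 4 among initiators. Neither supports WP7's wording about the target population, because changes in non-starters and in established users are not observed.

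The illustrated size is a 7.6% fall in VTE with no change in the initiator rate (6.0–8.3% over the table's rates), if 10% of would-be starters do not start. It rests on the Protocol's risk table and an assumed 10% reduction in starting. It shows what could be missed and does not forecast what happened. For the UK the remedy is mainly reconciliation, since the wider population is already identified in WP6 before the restriction and WP5 already uses that design.

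**What to change.** 1. **WP6:** follow all THIN women aged 18–49 who meet the two-year registration rule and have no previous VTE, with CHC status as a time-varying variable (non-use, new use, continuing use, switched, stopped). Report the VTE rate per window overall and by status, and restore the Abstract's age-standardised comparison.
2. **WP4:** add VTE follow-up of the prevalent users and switchers already in the SFK extract, reported separately from new users because risk is concentrated early in use. Otherwise, limit the Dutch conclusion in WP4 and WP7 to CHC initiators.
3. **WP5 and WP6:** show VTE rates in non-users by age only as a supportive indicator of secular trend. State that non-users include pregnant and post-partum women, and women who did not start or who stopped because of the recommendation. The series is therefore itself affected by the intervention and is not a clean control.

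The cost is protocol wording and additional programming on women the data sources already hold. If WP4 is not widened, the stated Dutch conclusion becomes narrower.

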We will consider each CHC individually and, additional to the analysis of individual types of combined oral contraceptives, in our analysis, we will group CHC together according to generation (i.e., the second generation containing levonorgestrel/norgestimate and ethinylestradiol, the third generation containing gestodene/desogestrel and ethinylestradiol and the newer generations containing drospirenone and ethinylestradiol).

Analysis

For each calendar year, we provide estimates of the proportion of each oral contraceptive type and the number of switchers (from one type to another or to a different pill strength) overall and stratified by age at initiation of CHC (18-24, 25-29, 30-34, 35-39, 40-44 and 45-49 years).

We will estimate incidence rates of initiating CHC use per 1000 person years at risk including 95% confidence intervals for each calendar year using incident dispensation as the indicator of CHC initiation. Similarly, we will provide estimates of incidence rates of switching per 1000 person years at risk including 95% confidence intervals for each calendar year of the study period.

In order to assess the effects of the review on initiation as well as on switching of treatment (between January 2012- January 2014 and between February 2014- December 2015), we will perform segmented regression analysis, taking the two time periods into account.

For our analyses we will be using SAS version 9.2 or higher.

WP3

Objectives

To obtain the number and proportion of women initiating different types of oral contraceptives in UK between January 2012 to December 2015 and to investigate switching pattern using data from The Health Improvement Network (THIN) primary care database.

Methods

Study population

For the UK drug utilization study, we will make use of anonymised primary care data from when women consult their general practice to obtain oral contraceptives. For each calendar year of the study period (1 January 2012 to 31 December 2015) we will identify women who were between 18 and 49 years and have been registered for at least two years prior with one of the general practices that contributed data to THIN. Individuals with no oral contraceptives prescription prior to study entry (from 2010 onwards) will be followed up until they receive their first oral contraceptive prescription, they become 50 years of age, 31 December 2015, or leave the practice. The new users are defined as women with no prior prescription of CHC in the two years before.

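### UK end-of-follow-up rules for initiation (WP3) and VTE (WP6) omit the end of the practice's data contribution to THIN; if practices stop before 31 December 2015, later UK rates are biased downward

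*Protocol*

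**What the plan says.** All places are in Protocol section 9.2.

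- **WP6, study population (VTE).** Women started on CHC with no earlier VTE record are followed to a first VTE record or until "they become 50 years of age, 31 December 2015 or they de-register with the general practice, whichever comes first".
- **WP3, study population (initiation).** Women without an oral contraceptive prescription are followed to their first one, or until "they become 50 years of age, 31 December 2015, or leave the practice".
- **Entry, both work packages.** A woman must "have been registered for at least two years prior with one of the general practices that contributed data to THIN". No dates are attached to the contribution, and nothing requires the practice to be still contributing during follow-up.
- **WP3, switching cohort.** This list has an extra stop: "Prevalent users will be followed until switch of treatment, six months after last prescription, becoming 50 years of age, December 31st 2015", followed by leaving the practice and death.
- **Denominators.** For initiation: "We will tabulate the estimates of new users by 1000 person years at risk including 95% confidence intervals for each calendar year". For VTE: "We will tabulate the estimates of incident VTE by 10 000 person years at risk including 95% confidence intervals for each calendar year". WP6 also calculates incidence among new users separately for the two windows.

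Section 9.5 (limitations) does not discuss practices entering or leaving THIN.

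**The concern.** In the UK part, both the exposure and the outcome exist only as entries in the records of contributing practices. Once a practice stops contributing, its women can no longer produce a recorded initiation or VTE. Such a woman has neither left nor de-registered, so the written lists keep her in the denominator until age 50 or 31 December 2015. Time is added to the denominator and nothing can be added to the numerator.

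The share of empty time grows with calendar time, so it weighs more on February 2014 – December 2015 than on January 2012 – January 2014. A before/after contrast of rates would move downward with no change in prescribing or in VTE. WP7 intends the report to show whether the recommendation worked and whether it changed VTE incidence. A spurious fall would be read as success.

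**Working it through.** **Figures in the protocol.** It states no UK person-time, event count or practice-loss rate, so there is no figure to reproduce. The windows come from the research question: 25 months (January 2012 – January 2014) and 23 months (February 2014 – December 2015), 48 in all.

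**Assumption.** A fraction f of practices stops contributing, at times spread uniformly over the 48 months. True rates are constant, and other exits are ignored. Any post/pre ratio different from 1 is then spurious.

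**WP3 initiation: women at risk from January 2012.**
- Unobserved share, window 1: f × (25/48) × 0.5 = 0.26f.
- Unobserved share, window 2: f × (25/48 + 0.5 × 23/48) = 0.76f.
- Spurious ratio: (1 − 0.76f)/(1 − 0.26f).
- At f = 20%: 0.848/0.948 = 0.89.

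**WP6 VTE: initiators entering over time.** A woman can be seen to initiate only while her practice contributes, so the WP3 formula would overstate the effect here. Let t be time as a fraction of 48 months and a = 25/48 = 0.521 (a² = 0.271, a³ = 0.141). Women enter at a constant rate from practices still contributing and are kept to the end of 2015.
- Observable person-time at t is proportional to t(1 − ft).
- Counted person-time at t is proportional to t − ft²/2.
- Window 1 observed share: (a²/2 − fa³/3)/(a²/2 − fa³/6).
- Window 2 observed share: ((1 − a²)/2 − f(1 − a³)/3)/((1 − a²)/2 − f(1 − a³)/6).
- At f = 20%: 0.1262/0.1309 = 0.964 and 0.3071/0.3357 = 0.915, so the ratio is 0.949.

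| f (assumed) | WP3 observed share, windows 1 and 2 | WP3 spurious ratio | WP6 observed share, windows 1 and 2 | WP6 spurious ratio |
|---|---|---|---|---|
| 0% | 1.000, 1.000 | 1.00 | 1.000, 1.000 | 1.00 |
| 10% | 0.974, 0.924 | 0.95 | 0.982, 0.959 | 0.98 |
| 20% | 0.948, 0.848 | 0.89 | 0.964, 0.915 | 0.95 |
| 30% | 0.922, 0.772 | 0.84 | 0.945, 0.866 | 0.92 |

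**Different loss model (constant annual loss).** The direction is the same. At 5% and 10% loss per year, the ratio is 0.90 and 0.81 for women at risk from January 2012, and 0.96 and 0.91 for initiators entering over time.

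**If contributing practices were re-selected each calendar year.** With annual loss L and h = −ln(1 − L), the observed share within each year is (1 − e^(−h))/h. This is 0.975 at L = 5% and 0.949 at L = 10%, the same every year. Rates would be about 2.5% or 5.1% too low throughout, with no artificial decline.

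**The case against.** Several objections have force.

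- **No practice is said to have left.** A reader might infer that later UK rates will fall artificially. The documents do not support that: no section says that any practice stopped contributing before 31 December 2015, and at zero loss there is no bias. The point is therefore conditional. What stands is that an end-of-follow-up rule should not depend on zero loss.
- **Yearly selection.** Both work packages say: "For each calendar year of the study period (1 January 2012 to 31 December 2015) we will identify women who were between 18 and 49". If this means a fresh selection of contributing practices each year, the trend disappears and a small, even deficit remains. The text does not say so, and its stated end of follow-up is 31 December 2015, not the end of each year.
- **Women using CHC.** WP6 tabulates rates among women using CHC, so a woman with no further prescriptions might be dropped. But the WP6 exit list contains no end of use.
- **Steady drift and segmented regression.** Uniform stopping lowers the WP3 initiation rate along a straight line. A segmented regression with a pre-Decision slope would absorb that. It would not absorb stopping concentrated in one period, and WP6 describes no trend term for its two-window VTE rates.
- **Unaffected results.** The six-month rule limits empty time in the switching cohort. Generation shares have initiators, not person-time, as denominator. It would be wrong to extend the point to either.
- **Look-back.** A reader might also infer that the two-year new-user look-back can fall in a period without data, because entry rests on registration. The protocol does not describe how THIN holds past records, so neither direction nor size can be given.
- **Left to an analysis plan.** An analysis plan that is not shown may name the last data date. The protocol nevertheless writes out exit rules that read as complete, and WP6 closes its list by taking whichever event comes first.

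**Conclusion.** The defect is real but conditional. The WP3 initiation and WP6 VTE lists stop follow-up at the outcome, age 50, 31 December 2015 or the woman's departure from the practice, and omit the end of the practice's contribution. It would be inaccurate to say that follow-up ends only when the woman leaves.

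If practices stop contributing before the end of 2015, the rules as written bias the later UK rates downward. For an assumed 10% to 30% stopping uniformly over 48 months, the spurious post/pre ratio runs from about 0.95 to 0.84 for WP3 initiation and from about 0.98 to 0.92 for WP6 VTE, roughly half the bias. These figures also assume constant true rates, follow-up run to 31 December 2015 as written, and no yearly re-selection of practices. The change should be made, since the error would favour the conclusion that the recommendation succeeded and it is easily prevented.

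**What to change.** Add *the date of the practice's last data contribution to THIN* to the end-of-follow-up lists in WP3 and WP6. As a sensitivity analysis, repeat the pre/post comparison in practices that contributed throughout 2012–2015.

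The cost is one clause in each of two work packages, and a practice-level end date in the extract. Nominal UK person-time falls slightly, but all of the time removed by the clause is time in which nothing could have been recorded. Under the assumptions above, counted time then equals observed time, and a constant true rate gives a ratio of 1.00.
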